10.1 Missed Bolus Doses (MBD)

Missed bolus doses will be identified by using the CGM and Pen data.

2.

3.

4.

CCI

CCI

10.2 Percent Time-in-Range of Glucose

[figure not shown]
The percent time-in-range of glucose (> 70 and ≤ 180 mg/dL) will be calculated based on CGM data collected in the study period and summarized for each period by descriptive statistics.

A large black rectangular redaction box covering the text in this section.

10.3 Missed and Suboptimal Bolus Dose (MSBD)

The suboptimal bolus doses will be identified by using the CGM and Pen data.

A large black rectangular redaction box covering the text in this section.

CCI

10.4 Glycated Hemoglobin (HbA1c) Results

The HbA1c results (%) at each scheduled visit will be summarized by descriptive statistics.

10.5 Hypoglycemic Confidence Scale (HCS)

This evaluation uses the Likert scale with ratings of not confident at all, a little confident, moderately confident, and very confident to rate a subject's response to 9 items during the evaluation (8 items for subjects without a partner and 9 for subjects with a partner). Each item will receive a score from 1 to 4 based on the subject's response. HCS score is calculated as the sum of the item scores divided by the number of items completed.

The results on the Likert scale in the four categories will be summarized by descriptive statistics using frequency and percentage. The HCS score and the change from baseline will be summarized respectively.

The change from baseline to end of the period in HCS score vs. the percent time-in-range of glucose in the period will be graphically presented by a scatterplot.

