Study F3Z-MC-IOQV (IOQV) is a 12-week, multicenter, single-arm, outpatient, exploratory study with 2 study periods in subjects with T1D or T2D, respectively, using an investigational reusable insulin injection pen and a commercially available CGM device. Subjects participating in the study will follow an appropriate prescribed bolus insulin regimen suitable for their disease state using insulin lispro 100 units/mL injected via the reusable insulin injection pen. During the study, subjects will have their glucose monitored via a commercially available CGM device, which will be blinded during Study Period 1 and unblinded during Study Period 2. The main purpose of the study is to estimate missed bolus insulin doses in subjects with T1D or T2D.

Treatment Arm and Duration:

Study IOQV is a 12-week study with a single treatment arm. All subjects will administer insulin lispro U-100 (100 units/mL) using the investigational reusable insulin injection pen. All subjects will use a commercially available CGM device during the study.

Number of Subjects:

Screened: 80 subjects

Enrolled: 68 subjects

Completed: 50 subjects

Statistical Analysis:

The primary objective of Study IOQV is to objectively measure missed bolus doses in subjects with T1D or T2D with blinded CGM. The primary endpoint is the average number of days per month with a missed bolus dose, which will be estimated along with the 95% confidence interval. Secondary analyses will estimate the average number of days per month with a missed bolus dose with unblinded CGM, the percent time in glucose range, the percent of missed bolus doses, and the missed and suboptimal bolus dose (MSBD) by blinded and unblinded CGM. Exploratory analyses will evaluate the correlation between MSBD and CGM alert settings; graphically explore subject characteristics associated with short-term glycemic control; estimate

the average number of days per month with a missed bolus dose by type of diabetes (T1D, T2D) and CGM (blinded, unblinded).

Given the exploratory nature of Study IOQV, the analyses will be primarily descriptive. These will include mean, standard deviation, minimum, median, and maximum for continuous variables, and frequency and percentage for categorical variables.

2. Schedule of Activities

Table IOQV.1. Schedule of Activities

Procedure Weeks from Enrollment	Study Period 1 Blinded CGM			Study Period 2 Unblinded CGM		Early D/C	Notes
	Screening/ Enrollment V1 0W	V2 3W	V3 6W	V4 9W	End of Study V5 12W		

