
 To assess the association between MSBD rate and CGM alert settings To evaluate characteristics associated with short-term glycemic control in subjects with type 1 or type 2 diabetes To estimate the average number of days per month with a missed bolus dose in subjects with type 1 diabetes with 
 Blinded CGM Unblinded CGM To estimate the average number of days per month with a missed bolus dose in subjects with type 2 diabetes with 
 Blinded CGM Unblinded CGM 	
 Correlation between MSBD rate and CGM alert settings Outcome for each PRO instrument* The average number of days per month with a missed bolus dose The average number of days per month with a missed bolus dose

Abbreviations: CGM = continuous glucose monitoring; PRO = patient-reported outcomes.

* if available for use

5. Study Design

[figure not shown]

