5.1. Overall Design

Study IOQV is a 12-week, multicenter, single-arm, outpatient, exploratory study with 2 study periods in subjects with T1D or T2D. Study IOQV will use an investigational pen injector, which captures bolus insulin doses, and a commercially available CGM device. Subjects participating in the study will follow an appropriate prescribed insulin regimen suitable for their disease state using insulin lispro 100 units/mL injected via the pen. During the study, subjects will have their glucose monitored via the CGM device, which will be blinded during Study Period 1 and unblinded during Study Period 2. In addition, subjects will take PRO evaluations to assess potential behaviors related to short-term glycemic control.

Study governance considerations are described in detail in [Appendix 2](#).

One study center will be managed by Sponsor designee **CCI**, using telemedicine, mobile study nurses, and an electronic application called **CCI**. Further details about management of this study center by **CCI** are provided in [Appendix 4](#).

[Figure IOQV.1](#) illustrates the study design.

*Pen and Continuous Glucose monitor (CGM) Data collection

Note: All visits are in clinic/home

Figure IOQV.1. Illustration of study design for Clinical Protocol F3Z-MC-IOQV.

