10.3.4. Other Analyses

Patient reported outcomes rated on the Likert scale will be summarized using frequency and percentage. Domain or total scores will be summarized using: n, mean, SD, minimum, median, maximum at the times outlined in the SOA ([Table IOQV.1](#)).

In addition, bolus dose, basal insulin dose information, and exposure will be summarized.

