8.5 Big Five Inventory (BFI)

The BFI is a 44-item inventory that measures an individual on the Big Five Factors (dimensions) of personality, Extraversion versus introversion (8 items), Agreeableness versus antagonism (9 items), Conscientiousness versus lack of direction (9 items), Neuroticism versus emotional stability (8 items), and Openness versus closedness to experience (10 items). The evaluation uses a Likert scale of (1) disagree strongly, (2) disagree a little, (3) neither agree nor disagree, (4) agree a little, and (5) agree strongly.

The results on the Likert scale in the five categories will be summarized by descriptive statistics using frequency and percentage.

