11.2 Figures

The figures of the change from baseline for these patient-reported outcomes vs. percent time-in-range of glucose will be generated for each period.

Number	Title	Population
14.2.3.2	Scatterplot of Hypoglycemic Confidence Scale (HCS) Score vs. Percent Time-in-Range of Glucose	Evaluable
14.2.3.3	Scatterplot of Adult Low Blood Sugar Survey (ALBSS) Total Score vs. Percent Time-in-Range of Glucose	Evaluable
14.2.3.4	Scatterplot of Health Problem Solving Scale (HPSS) Total Score vs. Percent Time-in-Range of Glucose	Evaluable
14.2.3.5	Scatterplot of PRISM Self Illness Separation vs. Percent Time-in-Range of Glucose	Evaluable
14.2.3.6	Scatterplot of General Life Stress Scale (GLSS) Total Score vs. Percent Time-in-Range of Glucose	Evaluable

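### The only PRO figures in the SAP plot change in score against time-in-range level, so the exploratory objective on characteristics associated with glycemic control is only partly served

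*SAP*

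**What the plan says.** The objective is stated three times in the protocol. The exploratory objectives in section 4 include "To evaluate characteristics associated with short-term glycemic control in subjects with type 1 or type 2 diabetes". The Synopsis says the analyses will "graphically explore subject characteristics associated with short-term glycemic control". Section 5.1 says "subjects will take PRO evaluations to assess potential behaviors related to short-term glycemic control". The endpoint attached to the objective is simply the outcome of each PRO instrument, if available for use.

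SAP 10.5 carries this out with a scatterplot of "The change from baseline to end of the period in HCS score vs. the percent time-in-range of glucose in the period". SAP 10.6 to 10.9 apply the same rule to the ALBSS total, HPSS total, PRISM self illness separation and GLSS total. The lead sentence of SAP 11.2 confirms it: "The figures of the change from baseline for these patient-reported outcomes vs. percent time-in-range of glucose will be generated for each period". The titles beneath name the measure without mentioning change, for example "Scatterplot of Hypoglycemic Confidence Scale (HCS) Score vs. Percent Time-in-Range of Glucose".

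The BFI is scheduled at Visit 1 only. SAP 8.5 says of it: "The results on the Likert scale in the five categories will be summarized by descriptive statistics using frequency and percentage". Protocol 10.3.4 says of the PROs generally: "Domain or total scores will be summarized using: n, mean, SD, minimum, median, maximum at the times outlined in the SOA".

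**The concern.** A characteristic such as hypoglycemic confidence, problem-solving skill or personality is a level that a subject has. The natural plot for the stated objective is that level against time-in-range. The SAP instead puts change in the PRO on one axis and leaves time-in-range as a level on the other. That answers a different question: whether the relation between the PRO and time-in-range moved between Visit 1 and the end of the period.

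A PRO that is steadily related to glycemic control could then look unrelated to it in the only figure drawn. An instrument measured once cannot appear in a change plot at all. What is at stake is how well one exploratory objective is answered.

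**Working it through.** **1. What the listed outputs contain.** The lists in SAP 11.1 and 11.2 show no redaction, although parts of SAP 10.1 to 10.3 are blacked out.

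- All 5 plot rules (SAP 10.5 to 10.9) use change on the PRO axis and level on the time-in-range axis. The 11.2 lead sentence agrees, so six statements say change.
- All 5 titles in 11.2 omit change.
- Tables 14.2.3.1 to 14.2.3.5 summarize the five repeated PROs, and Table 14.2.2.2 summarizes time-in-range separately. No table crosses the two.
- The BFI appears in Tables 14.1.5.1 and 14.1.5.2 and in no figure.

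**2. What a change plot estimates.** Let Y0 be the baseline score (the screening/enrollment visit for both periods, SAP 7.2), Y1 the end-of-period score, and T percent time-in-range in the period. In the same subjects,

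slope of (Y1 − Y0) on T = Cov(Y1 − Y0, T) / Var(T) = b_end − b_base.

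This is an identity and needs no assumption about standard deviations. Equal slopes give a flat plot.

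**3. Correlation scale.** The documents give no correlations, so the inputs below are assumptions. With equal SDs at both visits, r0 and r1 the correlations of Y0 and Y1 with T, and rho the test-retest correlation,

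corr(Y1 − Y0, T) = (r1 − r0) / √(2(1 − rho)).

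| r0 | r1 | rho 0.5 | rho 0.7 | rho 0.9 |
|---|---|---|---|---|
| 0.4 | 0.4 | 0.00 | 0.00 | 0.00 |
| 0.3 | 0.4 | 0.10 | 0.13 | 0.22 |
| 0.2 | 0.4 | 0.20 | 0.26 | 0.45 |
| 0.4 | 0.3 | −0.10 | −0.13 | −0.22 |

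For example, (0.4 − 0.2)/√0.6 = 0.258. If the relation appears only after baseline (0 to 0.4, rho 0.7), the result is 0.4/√0.6 = 0.516 and the change plot shows it clearly. In the last row the change plot slopes downward although the level relation is positive at both visits.

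Unequal SDs alter this little. With k = SD(Y1)/SD(Y0), the formula is (k·r1 − r0)/√(1 + k² − 2k·rho). For r = 0.5 at both visits and rho 0.7, k = 0.9 gives −0.05/√0.55 = −0.067, and k = 1.1 gives 0.05/√0.67 = 0.061.

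**4. How visible a level relation would be.** The SAP plans no test or interval for these plots, so this is only a reading aid. At the planned 50 completers, the Fisher-z 95% interval around r = 0.4 is 0.14 to 0.61, and around r = 0.13 it is −0.15 to 0.39. If the level correlation is the same at both visits, the level interval would exclude 0 in about 28% (r = 0.2), 56% (0.3), 83% (0.4) and 97% (0.5) of studies. The change interval would exclude 0 in about 5%.

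**5. The BFI.** It is collected once, so it has no change from baseline and only a level plot could include it. Both documents give the number of items per dimension. Neither says which items belong to which dimension, which are reverse-keyed, or whether the score is a sum or a mean. SAP 10.7, by contrast, lists the items of every HPSS subscale.

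**The case against.** The strongest reply is that nothing promised is missing. The endpoint fixes neither level nor change, Protocol 9.1.3 says only that the PROs will possibly be explored, and the scatterplots are a graphical exploration. Change also suits a design in which CGM is unblinded after Visit 3 and five PROs are repeated at Weeks 6 and 12. Protocol 10.3.1 allows further exploratory analyses, and the SAP 11.3 listings already hold subject-level time-in-range, BFI and four of the five repeated PROs (the GLSS is not listed). Level plots could be made later without touching the SAP. All of this stands. It makes the point an improvement to the plan, with the modest gain that level plots specified now cannot be chosen after the data are seen.

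Four stronger readings are tempting, and the documents do not support them.

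- A reader might infer that text and titles conflict so badly that the programmer must guess. Six statements agree on change, so the intended variable is clear and the titles need only a labelling correction.
- A reader might infer that the change plots will be flat. That is the equal-slope case. Baseline scores precede the analysed windows (Visits 2 to 3 and 4 to 5) and, for Period 2, unblinding falls between, so slopes may well differ.
- A reader might infer that the protocol has been breached. The objective does not prescribe a level plot.
- A reader might take the unwritten BFI scoring rule as an error in its own right. It is missing detail. The sentence in Protocol 10.3.4 on domain or total scores is general and does not name the BFI, though it plausibly covers the five BFI dimensions.

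**Conclusion.** The point holds as a cheap improvement. The planned figures show how the relation between each PRO and time-in-range changed, not whether the PRO is related to time-in-range. No listed table or figure supplies the level relation, and the BFI is related to nothing. The exploratory objective is therefore only partly served.

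The slope identity is exact. The size of the loss rests on assumed correlations: the change plot carries nothing if the relation is stable, an expected correlation of about 0.26 if it moves from 0.2 to 0.4 at test-retest 0.7, and about 0.52 if it emerges from 0. No primary or secondary result is affected, and the documents rest no decision on these plots.

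**What to change.** - **SAP 10.5 to 10.9 and 11.2:** for each period, add scatterplots of PRO score level against percent time-in-range in that period. Use the baseline score, and the end-of-period score if wanted.
- **BFI:** add the five domain scores against time-in-range in each period. In SAP 8.5, summarize those scores with the statistics that Protocol 10.3.4 names, using the instrument's own scoring, and write that scoring down.
- **Existing plots:** keep them as supplementary and put change from baseline in their titles.
- **Labelling:** mark all of these figures exploratory and unadjusted for multiplicity.

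The cost is SAP wording, a BFI scoring algorithm, and added panels from data already collected. Baseline level gives 5 × 2 = 10 panels and the BFI 5 × 2 = 10. End-of-period level adds 5 × 2 = 10 if wanted. That is 20 to 30 panels beside the 10 change panels now planned.

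The downside is chance patterns. At n = 50 a true correlation of 0 gives a sample value beyond about ±0.28 in 5% of plots. If no association existed, 20 × 0.05 = 1.0 to 30 × 0.05 = 1.5 panels would look associated. For 30 panels the chance of at least one would be 1 − 0.95^30 = 0.79 if they were independent. They are not, because the same subjects supply every panel and both periods, so that last figure is only a rough guide.

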10.6 Adult Low Blood Sugar Survey (ALBSS)

This is an evaluation of the fear of hypoglycemia derived from the widely used and validated ALBSS. This evaluation uses the Likert scale of 0 ("never") to 4 ("almost always") to rate 11 items (Behavior domain with 5 items; Worry domain with 6 items). The behaviour domain score is the sum of the 5 item scores, and the worry domain score is the sum of the 6 item scores. The total score is the sum of the two domain scores (i.e. the sum of the 11 item scores).

The results on the Likert scale in the five categories will be summarized by descriptive statistics using frequency and percentage. The domain and the total scores and the change from baseline will be summarized respectively.

The change from baseline to end of the period in ALBSS total score vs. the percent time-in-range of glucose in the period will be graphically presented by a scatterplot.

10.7 Health Problem Solving Scale (HPSS)

The HPSS scale is a set of 50 items that the subject rates using a 5-point Likert scale ranging from “not at all true of me” (0 points) to “extremely true of me” (4 points). Seven subscale scores are calculated by summing scores for each item in the respective subscale. The HPSS total score is derived using the formula:

which sums the subscale averages, with reverse scoring of the negative subscales.

The seven HPSS subscale scores are:

Effective Problem Solving (EPS) = sum of scores of items 7, 9, 13, 20, 21, 24, 28, 44, and 49;

Impulsive/Careless Problem Solving (IPS) = sum of scores of items 8, 12, 27, 30, 38, 39, 41, and 42;

Avoidant Problem Solving (APS) = sum of scores of items 4, 25, 31, 33, 43, 46, and 48;

Positive Transfer/Learning (PTR) = sum of scores of items 5, 16, 19, 45, and 50;

Negative Transfer/Learning (NTR) = sum of scores of items 2, 3, 10, 14, 17, 23, 26, 29, 35, 37, and 40;

Positive Motivation/Orientation (PMO) = sum of scores of items 1, 6, 18, 32, and 36;

Negative Motivation/Orientation (NMO) = sum of scores of items 11, 15, 22, 34, and 47.

The results on the Likert scale in the five categories will be summarized by descriptive statistics using frequency and percentage. The HPSS subscale scores and the total score and the change from baseline will be summarized respectively.

The change from baseline to end of the period in HPSS total score vs. the percent time-in-range of glucose in the period will be graphically presented by a scatterplot.

10.8 Pictorial Representation of Illness and Self Measure (PRISM)

The data collected on the CRF PRISM Revised II will be summarized by descriptive statistics, including Self Illness Separation (mm) and the Illness Perception Measure (small, medium, and large) for the subject's diabetes today and the goal.

The change from baseline in self illness separation will be summarized by descriptive statistics as well. The shift from baseline in illness perception measure will be generated.

The change from baseline to end of the period in self illness separation vs. the percent time-in-range of glucose in the period will be graphically presented by a scatterplot.

10.9 General Life Stress Scale (GLSS)

The GLSS assesses the degree of stress an individual is currently experiencing in 6 general areas of life (work/household chores, friends/social activity, family, money/financial, housing/neighbourhood, and health), with five response options ranging from “not at all stressful” (score = 0) to “extremely stressful” (score = 4). The total score is the sum of the 6 individual scores.

The results of the 6 general areas of life in the five categories will be summarized by descriptive statistics using frequency and percentage. The GLSS total score and the change from baseline will be summarized respectively.

The change from baseline to end of the period in GLSS total score vs. the percent time-in-range of glucose in the period will be graphically presented by a scatterplot.

11. LIST OF TABLES AND DATA LISTINGS

11.1 Statistical Tables

The statistical tables will be generated using SAS[®] version 9.4. The sample size (n) and frequency (count) will be presented by whole number. The mean, standard deviation, median, minimum, and maximum will be rounded to one decimal place. The percentage will be presented to one decimal place.

Number	Title	Population
14.1.1	Subject Disposition	Screened
14.1.2.1	Demographics and Baseline Characteristics	Entered

Number	Title	Population
14.1.2.2	Demographics and Baseline Characteristics	Evaluable
14.1.3.1	Medical History	Entered
14.1.3.2	Medical History	Evaluable
14.1.4.1	Diabetes Diagnosis	Entered
14.1.4.2	Diabetes Diagnosis	Evaluable
14.1.5.1	Big Five Inventory	Entered
14.1.5.2	Big Five Inventory	Evaluable
14.1.6	Treatment Compliance	Evaluable
14.2.1*	Missed Bolus Dose	Evaluable
14.2.2.1.1	Number of Missed Bolus Doses per Month by HbA1c	Evaluable
14.2.2.1.2	Number of Missed Bolus Doses per Month by Duration of Diabetes	Evaluable
14.2.2.2	Percent Time-in-Range of Glucose	Evaluable
14.2.2.3	Missed or Suboptimal Bolus Dose	Evaluable
14.2.2.4	Glycated Hemoglobin (HbA1c) Results	Evaluable
14.2.3.1	Hypoglycemic Confidence Scale (HCS)	Evaluable
14.2.3.2	Adult Low Blood Sugar Survey (ALBSS)	Evaluable
14.2.3.3	Health Problem Solving Scale (HPSS)	Evaluable
14.2.3.4	Pictorial Representation of Illness and Self Measure (PRISM)	Evaluable
14.2.3.5	General Life Stress Scale (GLSS)	Evaluable
14.2.3.6.1	Number of Days per Month with Missed Bolus Dose in Subjects with Type 1 Diabetes	Evaluable
14.2.3.6.2	Number of Days per Month with Missed Bolus Dose in Subjects with Type 2 Diabetes	Evaluable
14.3.1.1	Number of Subjects with Adverse Events	Safety
14.3.1.2	Number of Adverse Events	Safety
14.3.1.3	Number of Subjects with Adverse Events by MedDRA System Organ Class / Preferred Term	Safety
14.3.1.4	Number of Subjects with Adverse Events by MedDRA System Organ Class / Preferred Term and Severity	Safety
14.3.1.5	Number of Subjects with Insulin Related Adverse Events by MedDRA System Organ Class / Preferred Term	Safety
14.3.1.6	Number of Subjects with Pen Related Adverse Events by MedDRA System Organ Class / Preferred Term	Safety
14.3.1.7	Number of Subjects with CGM Related Adverse Events by MedDRA System Organ Class / Preferred Term	Safety
14.3.1.8	List of Adverse Events Leading to Withdrawal from the Study	Safety
14.3.1.9	List of Serious Adverse Events	Safety
14.3.1.10	List of Death (if there is any)	Safety

Number	Title	Population
14.3.1.11	Number of Subjects with Non-Serious Adverse Events by MedDRA System Organ Class / Preferred Term	Safety
14.3.5.1	Bolus Insulin Regimen and Dose Changes	Safety
14.3.5.2	Concomitant Medication	Safety

* include the summaries of the number of days per month with MBD, percent of missed bolus doses, and number of MBD per day.

